8.6.1. MRI

MRIs of each of the 3 dimples selected for MRI and biopsy (Dimples 1, 2, and 3) will be performed on all subjects at times outlined in the Schedule of Activities (Section 1.2). Screening, Day 71, and Day 251 MRIs may be repeated as often as necessary to obtain an evaluable image. Repeat screening MRIs must take place within the screening window. MRIs must be completed prior to the required biopsies. Specific instructions for the MRI procedures will be provided in the Clinical Operations Study Manual.

All MRIs from this study are the property of Endo and de-identified images may be utilized for clinical development, scientific communication, marketing, regulatory purposes, and/or legal applications as required/desired by Endo.

8.6.2. Double Punch Biopsy

Subjects will have a total of three 8 mm double punch biopsies done, 1 in each of the 3 dimples selected for MRI and biopsy (Dimples 1, 2, and 3) at the times outlined in the Schedule of Activities (Section 1.2). Detailed directions of the collection, processing, storage, handling and shipment of the biopsy samples will be provided in the Clinical Operations Study Manual. The investigator must examine and confirm sufficient healing of the biopsy site before dosing on Day 1.

Subjects who received all 3 doses of study drug prior to 18 March 2020 will have Day 71 and 251 biopsies, if willing to do so. Subjects who received less than 3 doses of study drug prior to 18 March 2020 will not have the Day 71 and Day 251 biopsies performed.

De-identified biopsy samples may be stored for a maximum of 5 years (or according to local regulations) following the last sample collection from the last subject last visit for the study at a facility selected by the sponsor to enable further analysis including to develop methods, assays, prognostics and/or companion diagnostics related to specify the intervention target, disease process, pathways associated with disease state, and/or mechanism of action of the study intervention.

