2.1. Study Rationale

The results from Phase 2 (buttock and thigh) and Phase 3 (buttock) studies show CCH 0.84 mg given per treatment area (1 buttock or 1 thigh) is an effective treatment for edematous fibrosclerotic panniculopathy (EFP, commonly known as cellulite) based on improvement in the severity of cellulite as determined by the Investigator and the subject. There were no safety concerns following 3 doses of 0.84 mg of CCH per treatment area. The majority of adverse events (AEs) occurred at the site of injection and resolved before the next scheduled treatment in these studies. The immunogenicity profile of CCH has been consistent across all studies.

The efficacy of CCH treatment on cellulite has been demonstrated in previous clinical studies using validated photonumeric scales. This study will capture the change from baseline after CCH treatment using the validated photonumeric scales and explore tissue level changes in the treatment areas (buttocks and thigh), both from histopathology and radiology perspectives.

COVID-19 Public Health Emergency Impact

The COVID-19 public health emergency has disrupted the conduct of clinical research throughout the world. At Endo Pharmaceuticals Inc. (Endo) ensuring the safety of clinical study participants is our primary concern. In addition, the integrity of data obtained from clinical trials must be ensured.

Endo initiated study EN3835-212 at a single investigational site in November of 2019. The first subject was dosed with CCH on 26 December 2019. On 18 March 2020, the investigational site suspended Study EN3835-212 due to the COVID-19 public health emergency. At that time, 7 subjects had received at least 1 dose of CCH in this study. Of those 7 subjects, 2 had completed the 3 doses required for the study and 1 subject had completed 2 doses. No subjects had completed all assessments required for the Day 71 Visit or beyond.

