4. STUDY DESIGN

4.1. Overall Design

This is a single-center, open-label, Phase 2a study to assess the safety and efficacy of CCH in adult women with moderate or severe EFP of the buttocks or thighs using photonumeric scales, MRI, and histopathology of tissues from the treated area. Approximately 19 subjects will be dosed in this study.

This study was suspended due to the COVID-19 public health emergency on 18 March 2020. When the study re-opens, subjects who had received less than 3 doses of CCH prior to 18 March 2020 will be allowed to continue in the study and may receive any remaining doses with Sponsor approval. These subjects will complete all remaining visits and assessments EXCEPT biopsies and biopsy follow-up visits, if willing to do so. These subjects will be included in the safety assessments for the study, but will not be included in the efficacy assessments. Subjects who received less than 3 doses prior to 18 March 2020 may elect to remain in the study without receiving additional doses.

Subjects who received all 3 doses of CCH prior to 18 March 2020, will be allowed to continue in the study and complete all remaining visits and assessments (including biopsies and biopsy follow-up visits), if willing to do so. These subjects will be included in the safety assessments for the study, but will not be included in the efficacy assessments. Subjects who received all 3 doses of CCH prior to 18 March 2020 may elect to remain in the study without completing the biopsies and biopsy follow-up visits.

An additional 12 subjects will be dosed in the study. These subjects will be included in the safety assessments, and all efficacy assessments will be based on the data from these 12 subjects. For the 12 subjects who receive their first dose of study drug after 18 March 2020, every attempt will be made to enroll an equal number of subjects across the 2 severity levels in both buttocks and thighs (eg, 3 subjects with moderate buttock cellulite, 3 subjects with severe buttock cellulite, 3 subjects with moderate thigh cellulite, and 3 subjects with severe thigh cellulite).

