9. STATISTICAL CONSIDERATIONS AND METHODS

9.1. Sample Size Determination

There was no formal sample size calculation for this study. A total of 12 subjects is considered sufficient to determine if biopsy will demonstrate changes in histopathology associated with CCH treatment while exposing the minimum number of subjects possible to the risks associated with this invasive procedure.

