9.2. Populations for Analysis

For the purposes of analysis, the following populations are defined:

- The Safety Population will include all subjects who have undergone the first (screening) biopsy.
- The Evaluable Population will include all subjects in the Safety Population who received their first dose of CCH in this study after 18 March 2020 and who had a baseline and at least 1 postinjection PR-PCSS evaluation.

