9.3.2. MRI and Biopsy Analyses

A descriptive summary of changes from baseline seen in MRI and biopsy results will be provided for the Evaluable Population.

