9.4. Interim Analysis

An interim analysis will be conducted when at least 4 of the 12 subjects who received their first dose of study drug after 18 March 2020 have completed their Day 71 visit. For all subjects who received their first dose of study drug after 18 March 2020, analysis of all primary, secondary,

and tertiary endpoints will be included in the interim analysis. For the subjects who received all three doses prior to 18 March 2020, their MRI and biopsy data, if available, will be assessed separately but included in interim analysis. The purpose of the interim analysis is to determine if changes in morphology and/or histology can be identified using MRI and biopsy. If the interim analysis does not indicate that such changes can be identified, subsequent or additional MRIs or biopsies will not be performed in this study.

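### Protocol 9.3.2 and SAP 7.8 name different populations for MRI and histology: one leaves out all 7 women first dosed before 18 March 2020, the other pools them with the 12 new women

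*Protocol*

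**What the plan says.** **Who was interrupted.** Protocol 2.1 reports the position when the site suspended on 18 March 2020: "At that time, 7 subjects had received at least 1 dose of CCH in this study". It continues: "Of those 7 subjects, 2 had completed the 3 doses required for the study and 1 subject had completed 2 doses". A further 12 women are to be dosed.

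**What is still collected.** For women with fewer than 3 doses, Protocol 4.1 says: "These subjects will complete all remaining visits and assessments EXCEPT biopsies and biopsy follow-up visits, if willing to do so". Their MRIs therefore stay, and Protocol 8.6.1 schedules MRI for every subject. For the three-dose women, Protocol 8.6.2 says "Subjects who received all 3 doses of study drug prior to 18 March 2020 will have Day 71 and 251 biopsies"; the sentence goes on to make this depend on their willingness, and 4.1 lets them stay in the study without biopsies.

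**What the protocol analyses.** Section 9.3.2: "A descriptive summary of changes from baseline seen in MRI and biopsy results will be provided for the Evaluable Population". Section 9.2 limits that population to women "who received their first dose of CCH in this study after 18 March 2020". Section 9.4 adds, for the three-dose women at the interim, that "their MRI and biopsy data, if available, will be assessed separately but included in interim analysis".

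**What the SAP analyses.** SAP 7.8, 7.8.1 and 7.8.2 plan a summary table and a listing of MRI and of histopathology, by treatment region, in the Safety Population. SAP 5 defines that population by having had a screening MRI or biopsy, with no condition on the date of first dose. SAP 8 states that the SAP rests on the original protocol and Amendment 1.

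**The concern.** The same secondary (Day 71) and tertiary (Day 251) tissue endpoints have two populations, and neither suits the interrupted women. Under the protocol they disappear from the final MRI and biopsy summary. Under the SAP they are mixed with women treated on schedule, with nothing in the table to show who had fewer doses or was assessed late.

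The trial asks whether tissue change after treatment can be seen at all, in about 12 women and without a formal sample size calculation. In so small a descriptive data set, a few off-schedule or partly treated women can change the picture. A plan that leaves inclusion open also lets it be settled after the images and slides have been read.

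**Working it through.** **Inputs.** From Protocol 2.1: 7 women dosed before the suspension, 2 with three doses and 1 with two. From 4.1: 12 new women, about 19 in total. From Table 1: post-treatment MRI at Day 71 (Dimples 2 and 3) and Day 251 (Dimple 3); post-treatment biopsy at Day 71 (Dimple 2) and Day 251 (Dimple 3); Day 71 window up to 10 days late.

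**The plan's own figure.** 7 + 12 = 19, which reproduces. Women with fewer than 3 doses: 7 − 2 = 5.

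**Procedures affected (maxima, since participation is voluntary and the interim may cancel later ones).**
- Three-dose women: 2 × 2 = 4 biopsies and 2 × 2 = 4 MRI visits.
- Women with fewer doses: 5 × 2 = 10 MRI visits and no post-treatment biopsies.
- All 7: 14 MRI visits, or 7 × 3 = 21 dimple images.

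**Where each set is analysed.**

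| Data | Protocol interim (9.4) | Protocol final (9.3.2) | SAP 7.8 |
|---|---|---|---|
| Three-dose women: 4 MRI visits, up to 4 biopsies | Yes, separately, if available | No | Yes, pooled by region |
| Other 5 women: up to 10 MRI visits | Not named | No | Yes, pooled by region |
| 12 new women | Yes | Yes | Yes, pooled by region |

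The SAP's own interim section (6.4) waits for all subjects to reach Day 71 and contains no separate assessment of the three-dose women.

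**Share of the SAP's pooled display.**
- Day 71 MRI: 7/19 = 36.8%.
- Day 71 histology: 2/(12 + 2) = 14.3%.
- Within one region the share is unknown, because the documents do not give the region of the 7. With 6 new women per region as planned (3 moderate + 3 severe), it runs from 0/6 to 7/13 = 53.8% for MRI, and from 0/6 to 2/8 = 25% for histology.

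**How far off schedule the three-dose women could be.** On 15 April 2020 all 7 were more than a week past their window. For the three-dose women the next visit was Day 71, whose window ends on Day 81. Day 81 was therefore 7 April at the latest, and Day 1 was 18 January 2020 at the latest (7 April − 80 days). If the site reopened on 30 April 2020 or later (an assumption; no date is given), their Day 71 tissue falls on Day 104 or later, and on Day 127 or later for a woman first dosed on 26 December 2019. Measured from a nominal Day 43 injection, that is at least 104 − 43 = 61 days instead of 71 − 43 = 28. This also assumes that their Day 71 MRI and biopsy were not already done; the protocol says only that nobody had completed every Day 71 assessment.

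**Could their Day 251 tissue miss the interim?** With Day 1 between 26 December 2019 and 18 January 2020, nominal Day 251 is 1 to 24 September 2020. The interim needs 4 new women past Day 71. If new dosing began on 1 June 2020 (an assumption), the earliest Day 71 is 10 August, before those samples. If it began on 1 September, it is 10 November, after them. Both orders are possible.

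**The case against.** The case on the other side has force.

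- **The data are not without a plan.** A reader might infer that invasive samples are taken with no planned final use. The documents do not support that. Protocol 9.4 gives the three-dose women's tissue a separate interim assessment, aimed at the trial's central question, and SAP 7.8 would both summarise and list it. SAP 6.1 also promises listings of all case report form data.
- **The biopsies are voluntary and few.** A reader might also infer a conflict with the sample size rationale in Protocol 9.1, which speaks of "exposing the minimum number of subjects possible to the risks associated with this invasive procedure". That does not follow. Amendment 3 removed post-treatment biopsies from 5 of the 7 women and left them optional for the other 2. The 10 MRI visits with no stated protocol use belong to women who have no post-treatment biopsy.
- **These data are not a unique view of late or lightly treated tissue.** The 12 new women have Day 251 MRI and biopsy of Dimple 3. Those who stop treatment early are encouraged to continue assessments. Interrupted women with fewer than 3 doses may receive the rest with sponsor approval.
- **Leaving off-schedule women out of the main summary is sound.** The timing calculation supports this.
- **The SAP is simply older.** Protocol 9.3 calls for a detailed plan to be finalised before the interim, so an update may already be intended.

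All of this stands, and it limits the point to a mismatch. It does not remove the mismatch: the SAP's inclusion of these women follows from its not knowing about the interruption, and it pools them without showing dose or timing. Nor does the statement in 4.1 that they are outside the efficacy assessments settle the matter, because the protocol places MRI and biopsy under pharmacodynamics (8.6), not efficacy (8.1).

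**Conclusion.** The point holds as a conflict between the documents with a limited gap inside the protocol. For the same MRI and histology endpoints, the protocol excludes all 7 interrupted women and the SAP pools all 7. The choice decides whether up to 37% of the women in the Day 71 MRI summary, and up to 14% in the Day 71 histology summary, were off schedule or incompletely dosed. Inside the protocol, three-dose tissue collected after the interim has no stated analysis, and up to 10 MRI visits in 5 women have none at any stage.

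The counts come directly from the documents and assume that every willing woman completes every procedure. The Day 104 figure depends on the assumed reopening date, and whether Day 251 samples miss the interim depends on when new dosing began.

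**What to change.** Reconcile Protocol 9.3.2 and 9.4 with SAP 5, 6.4 and 7.8 before the interim data are read:

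1. In SAP 5, adopt the Amendment 3 Evaluable Population, and in SAP 7.8 use it for the main MRI and histology summary, as Protocol 9.3.2 does.
2. In Protocol 9.3.2 and SAP 7.8, add a separate descriptive table and listing of all available MRI and histology data for subjects first dosed before 18 March 2020. Show the number of doses received and the actual days since the last injection at each assessment, and do not pool these subjects with the Evaluable Population.
3. In SAP 6.4, carry over the Amendment 3 interim trigger and the separate assessment of the three-dose women from Protocol 9.4.

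The cost is a few sentences in each document and one small display of up to 7 off-schedule subjects, which will be too few to interpret beyond description. No procedure is added.

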8.7. Genetics

Not applicable

8.8. Biomarkers

8.8.1. Immunogenicity Assessments

Serum samples will be collected at times outlined in the Schedule of Activities (Section 1.2) and will be tested for binding anti-AUX-I and anti-AUX-II antibody testing. When immunogenicity samples are required on a Treatment Day, the sample will be collected prior to study treatment administration. The samples also will be tested for neutralizing antibodies at times to be determined by the sponsor.

The serum samples obtained will be processed, stored and then shipped frozen on dry ice to Endo's appointed laboratory for the determination of anti-AUX-I and anti-AUX-II antibodies. Specific instructions for the collection, processing, storage, handling and shipment of the immunogenicity samples will be provided in the Clinical Operations Study Manual.

De-identified immunogenicity samples may be stored for a maximum of 5 years (or according to local regulations) following the last subject's last visit for the study at a facility selected by the sponsor to enable further analysis of immune responses to study treatment; develop methods, assays, prognostics and/or companion diagnostics related to specify the intervention target, disease process, pathways associated with disease state, and/or mechanism of action of the study the study treatment.

8.9. Medical Resource Utilization and Health Economics

Not applicable

9. STATISTICAL CONSIDERATIONS AND METHODS

9.1. Sample Size Determination

There was no formal sample size calculation for this study. A total of 12 subjects is considered sufficient to determine if biopsy will demonstrate changes in histopathology associated with CCH treatment while exposing the minimum number of subjects possible to the risks associated with this invasive procedure.

9.2. Populations for Analysis

For the purposes of analysis, the following populations are defined:

- The Safety Population will include all subjects who have undergone the first (screening) biopsy.
- The Evaluable Population will include all subjects in the Safety Population who received their first dose of CCH in this study after 18 March 2020 and who had a baseline and at least 1 postinjection PR-PCSS evaluation.

9.3. Statistical Hypotheses and Analyses

This section provides a general summary of the statistical methods to be used in analyzing study data. A more detailed statistical analysis plan will be developed and finalized prior to the interim analysis.

9.3.1. Efficacy Analysis

The primary endpoint of change from baseline in PR-PCSS at Day 71 will be summarized by treatment area (left or right) and region (buttock or thigh) using appropriate descriptive statistics using the Evaluable Population.

All secondary and tertiary PR-PCSS, CR-PCSS, and Hexsel efficacy endpoints will be summarized by treatment area (left or right) and region (buttock or thigh) using appropriate descriptive statistics using the Evaluable Population.

9.3.2. MRI and Biopsy Analyses

A descriptive summary of changes from baseline seen in MRI and biopsy results will be provided for the Evaluable Population.

9.3.3. Safety Analyses

All subjects who have undergone the first biopsy during screening will be included in the safety analyses.

9.3.3.1. Adverse Events

AEs will be coded using MedDRA by preferred term within system organ class. The number of AEs and the number of subjects reporting AEs will be listed and summarized descriptively by body system, preferred term, severity, and causality for each treatment group. Only TEAEs (events that are new in onset or aggravated in severity following treatment) will be included in all summaries. SAEs (including death) will be summarized.

9.3.3.2. Vital Signs and Laboratory Evaluations

Descriptive statistics will be presented for actual and change from baseline at each visit for vital signs and for each clinical laboratory test parameter.

9.3.4. Other Analyses

Anti-AUX-I and anti-AUX-II antibody levels will be summarized using descriptive statistics for the actual value at the visit. Samples from Day 1, Day 71, Day 161, and Day 251 visits will be analyzed for anti-AUX-I and anti-AUX-II antibodies and a subset of samples will be analyzed for neutralizing antibodies. Neutralizing antibody results, if tested, will be summarized as percentage of positive/negative.

9.4. Interim Analysis

An interim analysis will be conducted when at least 4 of the 12 subjects who received their first dose of study drug after 18 March 2020 have completed their Day 71 visit. For all subjects who received their first dose of study drug after 18 March 2020, analysis of all primary, secondary,

and tertiary endpoints will be included in the interim analysis. For the subjects who received all three doses prior to 18 March 2020, their MRI and biopsy data, if available, will be assessed separately but included in interim analysis. The purpose of the interim analysis is to determine if changes in morphology and/or histology can be identified using MRI and biopsy. If the interim analysis does not indicate that such changes can be identified, subsequent or additional MRIs or biopsies will not be performed in this study.

10. SUPPORTING DOCUMENTATION AND OPERATIONAL CONSIDERATIONS

10.1. Appendix 1: Regulatory, Ethical and Study Oversight Considerations

10.1.1. Regulatory and Ethical Considerations

This clinical study is designed to comply with the ICH Guidance on General Considerations for Clinical Trials (62 FR 6611, December 17, 1997), Nonclinical Safety Studies for the Conduct of Human Clinical Trials for Pharmaceuticals (62 FR 62922, November 25, 1997), Good Clinical Practice: Consolidated Guidance (62 FR 25692, May 9, 1997) and 21 CFR parts 50, 54, 56 and 312.

The study will be conducted in full compliance with ICH E6, the Food and Drug administration (FDA) guidelines for good clinical practices (GCP) and in accordance with the ethical principles that have their origins in the Declaration of Helsinki defined in 21 CFR, 312.120.

Approval by the IRB/IEC prior to the start of the study will be the responsibility of the investigator. A copy of approval documentation will be supplied to Endo, along with a roster of IRB/IEC members that demonstrates appropriate composition or other documentation of assurance of appropriate composition per local and national regulations (eg, a Department of Health and Human Services [DHHS] Assurance Number will satisfy this requirement for IRBs in the United States).

The study protocol, the ICF, advertisements, materials being provided to subjects, and amendments (if any) will be approved to IRB/IECs at each study center in conformance with ICH E6, CFR Title 21 Part 56, and any other applicable local laws. The investigator is responsible for supplying the IRB/IEC with a copy of the current Investigator's Brochure, Package Insert, or Summary of Product Characteristics, as well as any updates issued during the study. During the course of the study, the investigator will provide timely and accurate reports to the IRB/IEC on the progress of the study, at intervals not exceeding 1 year (or as appropriate), and will notify the IRB/IEC of SAEs or other significant safety findings, per the policy of the IRB/IEC. At the conclusion of the study, the investigator will submit a final report or close out report to the IRB/IEC and provide a copy to Endo.

Any amendment to this protocol will be provided to the investigator in writing by Endo. No protocol amendment may be implemented (with the exceptions noted below) before it has been approved by the IRB/IEC and the signature page, signed by the investigator, has been received by Endo. Where the protocol is amended to eliminate or reduce the risk to the subject, the amendment may be implemented before IRB/IEC review and approval. However, the IRB/IEC

must be informed in writing of such an amendment and approval obtained within reasonable time limits. Deviating from the protocol is permitted only if absolutely necessary for the safety or clinical management of the subject, and must be immediately reported to Endo.

The investigator will be responsible for supplying updated safety and/or study information to study subjects as it becomes available.

